11.9.4 Infections

Tumor necrosis may be seen with the use of talimogene laherparepvec. The presence of necrotic or ulcerating lesions may pre-dispose the subject to local and/or systemic infections such as cellulitis, bacteremia, etc. Careful wound care and infection precautions are recommended if tumor necrosis results in open wounds.

12.0 CRITERIA FOR THERAPEUTIC RESPONSE/OUTCOME ASSESSMENT

12.1 Antitumor effect

All patients will undergo a baseline staging CT scan of the chest (with or without contrast), abdomen and pelvis (with contrast if renal function permits), and MRI abdomen/pelvis (with and without contrast) if deemed necessary by the treating physician. Response evaluations will occur at week 8 and every 8 weeks subsequently (\pm 1 week window) until 12 months, and then less frequently at the discretion of the treating investigator.

Response and progression will be evaluated in this study using the international criteria proposed by the revised Response Evaluation Criteria in Solid Tumors (RECIST) guideline, version 1.1 (Primary response criteria).⁸⁸ Changes in the largest diameter (unidimensional measurement) of the tumor lesions and the shortest diameter in the case of malignant lymph nodes are used in the RECIST criteria.

In addition, patients will also be evaluated using the Immune-related revised Response Evaluation Criteria in Solid Tumors (irRECIST),⁸⁹ which will not be used for treatment decisions (Secondary Response Criteria) and are discussed separately in section 12.12.

In subjects who have initial evidence of progressive disease (PD) as per RECIST criteria or irRECIST criteria, it is at the discretion of the investigator to continue a subject on study treatment until confirmation of $PD \geq 4$ weeks. This clinical judgment decision should be based on the subject's overall clinical condition, including performance status, clinical symptoms, and laboratory data.

Subjects will receive treatment if they are clinically stable as defined by the following criteria:

- Absence of signs and symptoms indicating PD.
- No decline in the Eastern Cooperative Oncology Group (ECOG) performance status
- Absence of rapid progression of disease
- Absence of progressive tumor at critical anatomical sites (e.g., cord compression) requiring urgent alternative medical intervention

12.2 Definitions

Evaluable for toxicity – All patients will be evaluable for toxicity from the time of their first treatment with talimogene laherparepvec and/or pembrolizumab.

Evaluable for efficacy – Only those patients who have a measurable disease based on RECIST 1.1 criteria will be eligible for this study, as highlighted in Section 6.0. These patients will have their response classified according to the definitions stated below.

Only those patients who have measurable disease present at baseline, have received at least one cycle of therapy, and have had their disease re-evaluated will be considered evaluable for response. (Note: Patients who exhibit objective disease progression prior to the end of cycle 1 will also be considered evaluable. Note: one cycle of therapy consists of 21 days where the study therapy (TVEC and pembrolizumab) is administered at the start of the cycle on day 1)

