12.6 Early death

If the patient has no repeat tumor assessments following initiation of study therapy resulting from the death of the patient due to disease or treatment, it is considered early death.

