12.7 Symptomatic Deterioration

Patients with global deterioration of health status requiring discontinuation of treatment without objective evidence of disease progression at that time be recorded as "symptomatic deterioration". Every effort should be made to document objective progression even after discontinuation of treatment.

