Patients evaluable for efficacy analysis will include all patients treated with talimogene laherparepvec or pembrolizumab and assessable for response. Patients who are missing an assessment of response post baseline will not be considered evaluable for response unless they missed the assessment due to progression of disease in which case they will be considered non-responders for that time point. Patients who miss an assessment of response post baseline for any reason other than progression of disease will be replaced.

Patients evaluable for safety analysis will include all patients who have received at least one dose of talimogene laherparepvec and pembrolizumab.

We expect to accrue approximately 1-2 patients each month and hence expect to finish enrollment in 10-20 months.

Additional cohorts:

Locally advanced/metastatic cohorts:

Primary End Point

The primary objective is to evaluate the efficacy of the combination therapy in each subtype-specific cohort, as assessed by the best objective response rate (complete response + partial response). The primary endpoint is best objective response rate (RECIST 1.1). It will be estimated for each subtype-specific cohort, as the proportion of evaluable patients who have complete response and partial response as defined by RECIST 1.1 criteria, with a two

sided 95% CI provided. The lower limit of the CI allowed by a sample size of 10 is provided for a range of possible ORR in the below table.

Table 15. 95% CI for estimating ORR for a Sample Size of 10 Patients

Estimated ORR	0.20	0.30	0.40	0.50
CI 95%	0.03~0.56	0.07~0.65	0.12~0.74	0.19~0.81

Patients evaluable for efficacy analysis will include all patients who have received at least one cycle of treatment with T-VEC and pembrolizumab and are assessable for response. Patients who are missing an assessment of response post baseline will not be considered evaluable for response unless they missed the assessment due to progression of disease or treatment related toxicities in which case they will be considered non-responders for that time point. Patients who miss an assessment of response post baseline for any reason other than progression of disease and treatment related toxicity will be replaced.

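### Section 12.2 removes from the ORR patients who die of sarcoma before any re-evaluation, whereas sections 13.0 and 14.1 count them as non-responders

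*Combined protocol and SAP*

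**What the plan says.** Section 12.2 restricts evaluability to patients with measurable disease who "have received at least one cycle of therapy, and have had their disease re-evaluated will be considered evaluable for response". The one exception it allows is that "Patients who exhibit objective disease progression prior to the end of cycle 1 will also be considered evaluable". The same paragraph states that "one cycle of therapy consists of 21 days". Section 12.1 sets the assessment schedule: "Response evaluations will occur at week 8 and every 8 weeks subsequently".

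Section 14.1, for the first 20 patients, treats a patient with no post-baseline assessment as non-evaluable "unless they missed the assessment due to progression of disease in which case they will be considered non-responders for that time point". Section 13.0 repeats this rule. Both sections then provide for replacement only where the reason for the missed assessment is something other than progression. For the subtype cohorts, section 14.1 widens the clause: "unless they missed the assessment due to progression of disease or treatment related toxicities in which case they will be considered non-responders".

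Two further definitions cover the patients in question. The label of early death is given in section 12.6, with this condition: "If the patient has no repeat tumor assessments following initiation of study therapy resulting from the death of the patient due to disease or treatment". Section 12.7 labels symptomatic deterioration, for patients with a global decline in health "requiring discontinuation of treatment without objective evidence of disease progression at that time be recorded as" such. Neither section says whether these patients belong in the ORR denominator.

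**The concern.** The 12.2 exception has two conditions that the 13.0/14.1 rule lacks: the progression must be objective, and it must occur within cycle 1. A patient who dies of sarcoma in week 5 without a scan or lesion measurement meets neither condition and has no re-evaluation. Section 12.2 excludes that patient; 13.0 and 14.1 keep the patient as a non-responder.

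These patients cannot be responders, so the disagreement works in one direction: following 12.2 can only raise the ORR. In the subtype cohorts the primary result is an estimated proportion of evaluable patients with a 95% CI and no test, so the meaning of evaluable decides the result. The same data could yield two different primary estimates, each defensible from the text.

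**Working it through.** **Timing.** Cycle 1 ends on day 21. The first scheduled evaluation is week 8: day 50 if that means the first day of week 8, day 56 if it means eight completed weeks. The gap is 50 − 21 = 29 days to 56 − 21 = 35 days, or four to five weeks, before the ±1-week window. During this gap the 12.2 exception no longer applies and no scan is yet due.

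**The rules side by side**, for a treated patient with measurable disease and no post-baseline re-evaluation:

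| Reason | 12.2 | 13.0 and 14.1, first 20 | 14.1, subtype cohorts |
|---|---|---|---|
| Sarcoma death after cycle 1 | Not evaluable | Non-responder, not replaced | Non-responder, not replaced |
| Sarcoma death in cycle 1, no objective progression | Not evaluable | Non-responder, not replaced | Unclear: at least one cycle is also required |
| Symptomatic deterioration | Not evaluable | Not explicit; replaceable if not attributed to progression | Not explicit; same |
| Treatment-related toxicity | Not evaluable | Not evaluable, replaced | Non-responder, not replaced |

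The first row is a direct contradiction, as is the toxicity row for the subtype cohorts. The symptomatic-deterioration row is a gap.

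**The plan's own figure.** Inputs from 14.1: n = 20, success at 3 or more responders, null rate 5%, target rate 30%. Exact binomial at 5%:

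P(X ≥ 3) = 1 − 0.95^20 − 20(0.05)(0.95^19) − 190(0.05²)(0.95^18) = 1 − 0.35849 − 0.37735 − 0.18868 = 0.0755.

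Power at 30% is 0.9645, so the type II error is 0.0355. These round to the stated 0.08, 96% and 0.04.

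**Effect on the estimate.** With x responders among N treated and k patients dropped under 12.2 without replacement, the ORR moves from x/N to x/(N − k), a relative increase of N/(N − k). The documents give no value for k, so a range is assumed. Intervals are exact 95% CIs.

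N = 20, x = 6 (matching the 30% at 24 weeks in section 4.1, if its denominator was 20):

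| k | ORR | 95% CI |
|---|---|---|
| 0 | 6/20 = 30.0% | 11.9 to 54.3 |
| 1 | 6/19 = 31.6% | 12.6 to 56.6 |
| 2 | 6/18 = 33.3% | 13.3 to 59.0 |
| 3 | 6/17 = 35.3% | 14.2 to 61.7 |
| 4 | 6/16 = 37.5% | 15.2 to 64.6 |

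Subtype cohort, N = 10: with x = 2 and k = 2, 2/10 = 20% becomes 2/8 = 25%. With x = 3, 30.0% (6.7 to 65.2) becomes 3/9 = 33.3% (7.5 to 70.1) for k = 1 and 3/8 = 37.5% (8.5 to 75.5) for k = 2.

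**Effect on the test.** Dropping non-responders does not change the number of responders. Without replacement the 3-of-20 rule gives the same decision and its type I error stays at 0.0755.

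**The case against.** The strongest reply is that the biostatistics section and section 13.0 agree with each other, and an analyst would follow them rather than a definitions paragraph. That is likely, but no precedence is stated, and 12.2 is worded restrictively.

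A second reply is that few patients are affected. Section 12.2 asks for a re-evaluation, not specifically a week-8 CT. Section 12.3 accepts caliper measurement of superficial lesions, screening looks for a palpable injectable lesion, and Table 6 schedules physical examinations at weeks 4 and 7. Section 12.7 asks for every effort to document objective progression after stopping. This stands: only patients with no post-baseline measurement at all are caught.

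Three stronger readings are tempting, and the documents do not support them.

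- *The false-positive rate is inflated.* If a share e of patients were dropped and replaced until 20 were evaluable, a true 5% would act as 5%/(1 − e), and the type I error would be 0.085, 0.097 or 0.126 for e = 5%, 10% or 20%. But 12.2 has no replacement rule, and 13.0 and 14.1 do not allow replacement for progression. The inflation could arise only for symptomatic deterioration read as a reason other than progression.
- *Section 14.1 already counts every such patient as a non-responder.* It speaks of progression. Sarcoma death fits that directly. Symptomatic deterioration is not named, and 12.7 defines it by the absence of objective progression.
- *The reported ORR is biased.* The 35% and 30% in section 4.1 fit 7/20 and 6/20, that is, a full denominator. The documents do not say how many of the 20 lacked a re-evaluation. The 10 to 18 month median survival in section 3.1 gives an early-loss rate only under an assumed constant hazard, and it describes metastatic patients in general, whereas eligibility requires ECOG 0 or 1.

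**Conclusion.** The contradiction holds in the current text and should be removed. For sarcoma death before any re-evaluation, 12.2 and 13.0/14.1 place the same patient on opposite sides of the ORR denominator. For symptomatic deterioration the plan leaves the placement open. For treatment-related toxicity in the subtype cohorts, 12.2 again differs from 14.1.

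The consequence is a possible upward bias in the ORR: about 1.6 to 7.5 percentage points for 1 to 4 dropped patients with 6 responders among 20, and 5 points for 2 dropped in a cohort of 10 with 2 responders. The dropped counts are assumptions. The shifts are small beside the width of the confidence intervals, but they always go the same way. The design's type I error is not affected under the plan's replacement rules, and no actual bias in the reported results is shown.

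**What to change.** Replace the evaluability sentence and its note in 12.2 with the 13.0/14.1 rule, and name the cases, for example: *Treated patients with measurable disease at baseline who have no post-baseline re-evaluation because of death from disease, objective or clinical progression, or symptomatic deterioration, during or after cycle 1, are evaluable, count as non-responders and are not replaced.* Use the same wording in 13.0 and 14.1, so that symptomatic deterioration is no longer left to interpretation.

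For the subtype cohorts, carry the existing 14.1 clause on treatment-related toxicity into 12.2. Revise the 14.1 requirements for at least one cycle and for being assessable, so that they do not exclude a disease death during cycle 1.

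When reporting, state for the first 20 and for each cohort how many treated patients had no re-evaluation, and why.

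The cost is a few sentences and no new data. The reported ORR may be slightly lower.

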12.2.1 Disease Parameters

Measurable disease – Measurable lesions are defined as those that can be accurately measured in at least one dimension (longest diameter to be recorded for non-nodal lesions and short axis for nodal lesions) as >20mm by chest x-ray, as >10mm with CT scan or MRI, or >10mm with calipers by clinical exam. All tumor measurements must be recorded in millimeters (or decimal fractions of centimeters).

To be considered pathologically enlarged and measurable, a lymph node must be > 15 mm in short axis when assessed by CT scan (CT scan slice thickness recommended to be no greater than 5 mm). At baseline and in follow-up, only the short axis will be measured and followed.

Note: Tumor lesions that are situated in a previously irradiated area are not considered measurable unless there is evidence of progression after radiation therapy.

Non-measurable disease – All other lesions (or sites of disease), including small lesions (longest diameter <10mm or pathological lymph nodes with ≥ 10 to <15mm short axis) are considered non-measurable disease. Bone lesions, leptomeningeal disease, ascites, pleural/pericardial effusions, lymphangitis cutis/pulmonitis, inflammatory breast disease and abdominal masses (not followed by CT or MRI), are considered as non-measurable.

Target lesions – All measurable lesions up to a maximum of 2 lesions per organ and 5 lesions in total, representative of all involved organs, should be identified as target lesions and recorded and measured at baseline. Target lesions should be selected on the basis of their size (lesions with the longest diameter), be representative of all involved organs, but in addition should be those that lend themselves to reproducible repeated measurements. A sum of the diameters (longest for non-nodal lesions, short axis for nodal lesions) for all target lesions will be calculated and reported as the baseline sum diameters. The baseline sum diameters will be used as a reference to further characterize any objective regression in the measurable dimension of the disease.

Non-target lesions – All other lesions (or sites of disease) including any measurable lesions over and above the 5 target lesions should be identified as non-target lesions and should also be recorded at baseline. Measurements of these lesions are not required, but the presence, absence or in rare cases unequivocal progression of each should be noted throughout follow-up.

12.3 Methods for Evaluation of Measurable Disease

All measurements should be taken and recorded in metric notation using a ruler or calipers. All baseline evaluations should be performed as closely as possible to the beginning of treatment and never more than 4 weeks before the beginning of the treatment.

The same method of assessment and the same technique should be used to characterize each identified and reported lesion at baseline and during follow-up portion of study. Imaging-based evaluation is preferred to evaluation by clinical examination unless the lesion(s) being followed cannot be imaged but are assessable by clinical exam.

Clinical lesions - Clinical lesions will only be considered measurable when they are superficial (e.g., skin nodules and palpable lymph nodes) and ≥ 10 mm diameter as assessed using calipers (e.g., skin nodules).

Chest x-ray - Lesions on chest x-ray are acceptable as measurable lesions when they are clearly defined and surrounded by aerated lung. However, CT is preferable.

Conventional CT and MRI - This guideline has defined measurability of lesions on CT scan based on the assumption that CT slice thickness is 5 mm or less. If CT scans have slice thickness greater than 5 mm, the minimum size for a measurable lesion should be twice the slice thickness. MRI is also acceptable in certain situations (e.g. for body scans).

Use of MRI remains a complex issue. MRI has excellent contrast, spatial, and temporal resolution; however, there are many image acquisition variables involved in MRI, which greatly impact image quality, lesion conspicuity, and measurement. Furthermore, the availability of MRI is variable globally. As with CT, if an MRI is performed, the technical specifications of the scanning sequences used should be optimized for the evaluation of the type and site of disease. Furthermore, as with CT, the modality used at follow-up should be the same as was used at baseline and the lesions should be measured/assessed on the same pulse sequence. It is beyond the scope of the RECIST guidelines to prescribe specific MRI pulse sequence parameters for all scanners, body parts, and diseases. Ideally, the same type of scanner should be used and the image acquisition protocol should be followed as closely as possible to prior scans. Body scans should be performed with breath-hold scanning techniques, if possible.

12.3.1 Primary Response Criteria (RECIST 1.1)

12.3.1.1 Evaluation of Target Lesions

Complete Response (CR): Disappearance of all target lesions. Any pathological lymph nodes (whether target or non-target) must have reduction in short axis to <10 mm.

Partial Response (PR): At least a 30% decrease in the sum of the diameters of target lesions, taking as reference the baseline sum diameters.

Progressive Disease (PD): At least a 20% increase in the sum of the diameters of target lesions, taking as reference the smallest sum on study (this includes the baseline sum if that is the smallest on study). In addition to the relative increase of 20%, the sum must also demonstrate an absolute increase of at least 5 mm. (Note: the appearance of one or more new lesions is also considered progressions).

Stable Disease (SD): Neither sufficient shrinkage to qualify for PR nor sufficient increase to qualify for PD, taking as reference the smallest sum diameters while on study.

12.3.1.2 Evaluation of Non-Target Lesions

Complete Response (CR): Disappearance of all non-target lesions and normalization of tumor marker level. All lymph nodes must be non-pathological in size (<10 mm short axis).

Non-CR/Non-PD: Persistence of one or more non-target lesion(s).

Progressive Disease (PD): Appearance of one or more new lesions and/or unequivocal progression of existing non-target lesions. Unequivocal progression should not normally trump target lesion status. It must be representative of overall disease status change, not a single lesion increase.

Although a clear progression of “non-target” lesions only is exceptional, the opinion of the treating physician should prevail in such circumstances, and the progression status should be confirmed at a later time by the review panel (or MSKCC Principal Investigator).

12.3.1.3 Evaluation of Best Response

The best response is the best response recorded from the start of the treatment until disease progression/recurrence (taking as reference for progressive disease the smallest measurements recorded since the treatment started). The patient's best response assignment will depend on the achievement of both measurement and confirmation criteria.

Table 13. Evaluation of Best Response – RECIST criteria

Target Lesions	Non-Target Lesions	New Lesions	Best Response	Best Response for This Category also Requires:
CR	CR	No	CR	≥ 4 wks. Confirmation
CR	Non-CR/Non-PD	No	PR	≥ 4 wks. Confirmation
PR	Non-CR/Non-PD	No	PR	
SD	Non-CR/Non-PD	No	SD	documented at least once ≥ 4 wks. from baseline
PD	Any	Yes or No	PD	no prior SD, PR or CR
Any	PD*	Yes or No	PD	
Any	Any	Yes	PD	

* In exceptional circumstances, unequivocal progression in non-target lesions may be accepted as disease progression.

Note: Patients with a global deterioration of health status requiring discontinuation of treatment without objective evidence of disease progression at that time should be reported as "***symptomatic deterioration***." Every effort should be made to document the objective progression even after discontinuation of treatment.

12.4 Confirmation of response

Complete or partial response may only be claimed if the criteria for each are met at a subsequent time point (≥4 weeks later) in studies with a primary endpoint that include response rate.

12.4.1 Special note on target lesions that become “too small to measure”

While on study, all lesions (nodal and non-nodal) recorded at baseline should have their actual measurements recorded at each subsequent evaluation, even when very small (e.g. 2mm). However, sometimes, lesions or lymph nodes which are recorded as target lesions at baseline become so faint on CT scan that the radiologist may not feel comfortable assigning an exact measure and may report them as being “too small to measure”. When this occurs, it is important that a value be recorded on the D2M form. If it is the opinion of the radiologist that the lesion has likely disappeared, the measurement should be recorded as 0 mm. If the lesion is believed to be present and is faintly seen but too small to measure, a default value of 5 mm should be assigned.

